#### 8.5.6. Reporting of Events of Special Interest

Events of Special Interest are defined in Section 8.4 and should be reported to the Safety CRO within 24 hours of learning of its occurrence. For each of these events detailed surgical notes (with illustrative diagram), including reason for and outcome of any intervention or abandonment, should be completed within 48 hours and uploaded to the clinical database.

Detailed information about the occurrence and treatment/intervention for these events will be collected throughout the study up to 5 years post HAV implant. This information will include the following:

- Summarized surgical notes, including a simplified anatomical diagram showing where angioplasties, stents, or revisions have been performed (using intervention worksheet provided)
- Need for hospitalization (number of nights)
- Need for antibiotics (in the case of HAV-related infections)

#### 8.5.7. Follow-Up of Adverse Events

If any AEs are present when a subject completes 1 year post implant (Month 12) or ET, if earlier, or if a subject is withdrawn from the study, the subject will be re-evaluated within an appropriate period of time. At the investigator's discretion, minor AEs can be re-evaluated via telephone and documented. If the AE has still not resolved, additional follow-up will be performed as appropriate. The investigator or his designee should make every effort to contact the subject until the AE has resolved or stabilized or the medical monitor and investigator agree that further follow-up is not necessary. This should be documented in the subject's medical records.

# 8.6. Reporting of Pregnancy

If a study participant becomes pregnant during study participation, the participant will be withdrawn from the study and the event will be recorded as an adverse event in the eCRF. The

Confidential

site will also collect information about the pregnancy on the Pregnancy & Outcome Report Form (PORF), which must be submitted to the Safety CRO within 1 business day of completion. Complications experienced during the pregnancy will be recorded as AEs in the eCRF.

The participant will be asked to report the outcome of the pregnancy to the site. The site should collect the available outcome information and provide an updated PORF to the Safety CRO within 1 business day of receipt. If there is a congenital anomaly in the infant, this will be recorded as a SAE in the data forms for the mother (i.e., the study participant).

Partner pregnancies do not need to be reported.

# 8.7. Data Monitoring Committee

A Data Monitoring Committee (DMC) will review safety on an ongoing basis and provide recommendations about stopping, continuing or otherwise modifying the study. The DMC consists of individuals who are not directly involved in the conduct of the study. A charter describes the roles and responsibilities of the DMC. Responsibilities of the DMC will include review of aggregate safety data from other studies in the HAV clinical development program.

# 8.8. Interim Analysis and Stopping Criteria

This is a Phase 2 study with no formal interim analysis. Periodic reviews of safety data will be undertaken by the DMC with particular attention to events that might indicate structural failure of the HAV. Events that might have implications for already implanted HAVs and their possible removal - such as aneurysm formation (true or pseudo) or spontaneous rupture - will trigger a referral of the event urgently for DMC review

The DMC may recommend modification or early termination of the study for safety reasons.

# 9. STATISTICAL CONSIDERATIONS

This is a prospective, open label, single treatment arm, multicenter pilot study to evaluate the safety and efficacy of the HAV in patients with PAD undergoing femoro-popliteal bypass surgery. The primary objective of this study is to evaluate the safety and tolerability of the HAV in these patients and to determine the patency of the Humacyte HAV at 12 months post-implantation. The secondary objectives of this study are to further assess safety in terms of PRA response, and to determine the rates of HAV interventions required to keep the HAV patent. There is no formal hypothesis testing planned; the study involves only a single, open-label treatment group.

Endpoints will be assessed over a period of up to 60 months after HAV implantation. The primary analysis of the study will be conducted on the earlier of a) when the final subject enrolled reaches 12 months post-implant or b) all subjects enrolled in the initial 36 month accrual period have reached 12 months post-implant. Details of data handling and planned descriptive statistics are given in the Statistical Analysis Plan.

# 9.1. Analysis Population

All patients who receive an HAV will be included in the analyses. For discontinued or withdrawn patients, all available data will be included in the safety and efficacy analyses.

# 9.2. Safety Analyses

Safety analyses will be performed on all patients who have an HAV implanted when the final patient enrolled reaches 12 months post-implant

Incidence of HAV aneurysm formation (true or pseudo), anastomotic bleeding or spontaneous rupture, HAV infection, HAV removal, and significant local inflammation at the HAV implantation site will be separately tabulated and listed.

Adverse events will be coded using Medical Dictionary for Regulatory Activities (MedDRA) terms. Adverse events will be listed and summarized by system organ class, preferred term, incidence, severity, and duration. HAV complications will be listed in terms of incidence, severity, and (where appropriate) time to onset and duration. Serious adverse events will be summarized separately. Any premature discontinuations due to adverse events and deaths will be listed and summarized.

Laboratory data, including PRA, will be listed and summarized using appropriate descriptive statistics at each visit and for the absolute change from baseline values for all post-surgery visits. The closest non-missing values prior to surgery on Day 1 will be used as baseline values.

# 9.3. Efficacy Analyses

Primary, primary assisted, and secondary patency rates of the HAV at Month 12 and at all other post-surgery visits with evaluation of patency will be described.

Confidential

Primary patency is defined as the functional patency until any type of intervention; primary assisted patency is defined as an HAV still working without thrombosis; secondary patency is defined as the functional patency, with or without preceding successful interventional or surgical procedures to maintain or reestablish patency, until either final failure or the access is abandoned. Early discontinued patients prior to the visit of interest will be determined as being non-patent irrespective of the reason for discontinuation.

The rate and type of interventions needed to maintain / restore patency in the HAV will be descriptively tabulated.

The absolute change from baseline (Day 1) values to all post-surgery visits of duplex ultrasound parameters will be summarized. Summary statistics will also be provided at each time point.

The methods and endpoints regarding the efficacy parameters employed in this study are consistent with current clinical practice and are meaningful to the research community. Every attempt has been made to minimize the variability on the part of the surgeon when using this product. The results of this study will be used to determine the sample size of subsequent clinical studies.

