4.4 Efficacy Analysis

4.4.1 Analysis of Primary Efficacy Parameters

Efficacy Objective 1:

Primary, primary assisted, and secondary patency rates of the HAV at Month 12 with evaluation of patency will be described.

Primary patency is defined as the functional patency until any type of intervention.

Primary assisted patency is defined as an HAV still working without thrombosis.

Secondary patency is defined as the functional patency, with or without preceding successful interventional or surgical procedures to maintain or reestablish patency, until either final failure or the HAV is abandoned.

All patients start out in primary patency. A patient is not expected to flow from primary, to assisted, to secondary patency directly. For example, an abandonment can occur after the HAV implant, that ends the primary patency and the patient never went into an assisted or secondary status.

Primary patency	 Start: HAV implantation date End: earliest start date from assisted, secondary, or abandonment status
Primary assisted patency	 Start: any type of intervention to HAV End: earliest start date from secondary or abandonment status
Secondary patency	Start: earliest thrombosis AE start date;End: abandonment date

Many parts are used to derive patency:

Abandonment	 Source: AE eCRF Terms: "Anastomotic stenosis", "Arterial bypass stenosis" ,"Arterial bypass thrombosis", and "Arterial bypass occlusion" And action taken is recorded as "Patient withdrawn from study", or "None"
-------------	--

Final Analysis 14/23

Stenosis	 Source: AE eCRF Terms of "Anastomotic stenosis" "Arterial bypass stenosis"
Thrombosis	 Source: AE eCRF Terms of "Arterial bypass thrombosis" "Arterial bypass occlusion"
Interventions for stenosis	 Source: Interventions eCRF Intervention to treat stenosis: Intervention type on eCRF as "Intervention to treat anastomotic or mid-HAV stenosis but without HAV thrombosis.
Interventions for thrombosis	 Source: Interventions eCRF Intervention to treat thrombosis: Intervention type on eCRF as "Intervention to treat anastomotic or mid-HAV stenosis and with HAV thrombosis.
End of study	Source: End of study eCRF

Data handling for this rate will be as followed

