The assignment to a patency (yes/no) (primary, primary assisted, secondary patency) will be verified during the Data Review Meeting (DRM) using all data of CRF sections referring to HAV patency, clinical examination of the HAV site, doppler ultrasound assessment of HAV patency, HAV intervention, premature discontinuation, and AEs.

Patency rates will be presented with frequency tabulations showing patient numbers and patency rates for Month 12.

Clopper-Pearson confidence intervals (CI) will be presented for frequency counts of patency rates.

Kaplan-Meier (K-M) curves for primary, primary assisted, and secondary patency will be created at the 1-year report and for all subsequent reports. K-M curves will be provided using two censoring methods:

- a. Patients who die, withdraw from the study, or are lost to follow-up are censored at the day of the respective event.
- b. Patients who die, withdraw from the study, or are lost to follow-up are considered as having suffered failure of secondary patency at the day of the respective event.

Efficacy Objective #2:

Hemodynamically significant stenosis (>70% by duplex ultrasound criteria): The duplex ultrasound parameters will be summarized by planned visit up to Month 12.

- Frequency of stenosis occurrence, location of stenosis, and presence of aneurysm.
- Numeric summary of volumetric flow rate and inner diameter of HAV mid bypass.

A stenosis event can occur between planned study visits (i.e. Unscheduled Visits). A "by visit"

Statistical Analysis Plan	
CLN-PRO-004	

summary will represent the stenosis event/information that occurred before or on the planned visit. For example, the summary at Day 5 will denote the number of patients who had stenosis occur up to Day 5 or on the Day 5 visit. Similarly, the Day 29 summary will denote the number of patients with stenosis events that occurred after Day 5, and up to Day 29 (inclusive of Day 29).

The time of first stenosis (in days) will be summarized and calculated as number of days from HAV implantation to date of first stenosis event: Date of Stenosis – Date of Day 1 + 1. Patients who did not have a stenosis event will not contribute a value for this summary.

Please note, the clinical duplex will be recorded for all visits. Results after Month 12 **will not** be summarized in tables and will be provided in the listings.

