4.4.2 Analysis of Secondary Efficacy Parameters

Patency of the HAV (primary, primary assisted, secondary) rates will be presented for Months 3, 6 and 9.

Clopper-Pearson CIs will be presented for frequency counts of patency rates.

The HAV interventions and type of interventions needed to maintain / restore patency in the HAV through Month 12 will be descriptively summarized. Interventions will be recorded at each study visit and interventions occurring after the Month 12 visit will be provided in a listing.

Number of patients, who needed any intervention to maintain / restore patency throughout the study will be tabulated by counts and frequencies. The cumulative number of patients with any intervention needed will be presented stratified by visit and the number of patients having 1, 2, 3, etc. interventions will be presented.

Due to the nature of the study, an intervention can occur between planned study visits and will be recorded in the EDC as an unscheduled visit. A "by visit" summary will represent the intervention information that occurred before and on the scheduled visit. For example, the summary at Day 5 will denote the information from all interventions that occurred up to Day 5 visit and on the Day 5 visit. Similarly, the Day 29 summary will denote the information from all interventions that occurred after Day 5, and up to Day 29 (inclusive of Day 29).

VascuQol PAD symptom assessment data

The VascuQol PAD symptom assessment consists of 25 questions. The total score and the 5 domain scores (Activity, Symptom, Pain, Emotional, and Social) will be recorded in the clinical database. Total score and each domain score will be presented by descriptive measures for each visit as well as for the absolute change from baseline. Individual data, domain score and total score will also be listed.

The 1-year analysis will provide the table summary by planned visit up to Month 12. The final analysis will only display results in a listing.

ABI and 6 minute walk test

ABI and 6 minute walk test will be presented by descriptive measures for each visit as well as for the absolute change from baseline. Data will also be listed.

Statistical Analysis Plan	Final Analysis
CLN-PRO-004	16/23

The 1-year analysis will provide the table summary by planned visit up to Month 12. The final analysis will only display results in a listing.

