4.4.3 Analysis of Long Term Efficacy Parameters

Patient overall survival at 60 months

Patients overall survival (OS) status of alive or death, as well as the date of death and date of last known alive will be collected at the Month 60 visit.

OS is defined as: Date of Death or date of last known alive - Date of Surgery + 1

Patients who are still alive will be censored at the 60 month visit date or last known date alive, whichever occurs last. Median OS will be tabulated and Kaplan Meier (K-M) graph will also be included.

HAV interventions

HAV interventions will be listed.

Evidence of aneurysmal dilatation or stenosis of the HAV

Evidence of aneurysmal dilatation or stenosis of the HAV will be listed.

Patency of the HAV (primary, primary assisted, secondary)

Patency of the HAV (primary, primary assisted, secondary patency rates) will be presented for Months 18, 24, 30, 36, 42, 48, 54 and 60. Clopper-Pearson CIs will be presented for frequency counts of patency rates.

Limb salvage/amputation

Limb salvage/amputation at 18, 24, 30, 36, 42, 48, 54 and 60 months will be listed for all subjects who have not died, withdrawn, or been lost to follow-up.

Surgical Revascularization

Incidence of surgical revascularization of the implanted limb, at the level of the HAV or distal to HAV, will be listed for all patients who have not died, withdrawn, or been lost to follow-up.

VascuQol Quality of Life Questionnaire

VascuQol PAD symptom assessment consists of 25 questions. The total score and the 5 domain scores (Activity, Symptom, Pain, Emotional, and Social) will be recorded in the clinical database at 18, 24, 30, 36, 42, 48, 54 and 60 months. VascuQol results will be listed and summarized for all patients who have not died, withdrawn, or been lost to follow-up.

Final Analysis 17/23

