The data review will be conducted prior to final data base closure and can be done via a telephone conference or in writing. During the DRM it is to review and define patient's primary, primary assisted and secondary patency outcome (yes/no) and patient's time to loss of patency (primary, primary assisted and secondary). Additionally, adverse events of graft complications (aneurysm formation, anastomotic bleeding or rupture, graft infection and irritation/inflammation at the graft implantation site) will be identified.

For the data review meeting, ARG will provide patient data listings to the Sponsor, containing following information:

Statistical Analysis Plan	Final Analysis
CLN-PRO-004	22/23

- Any data on patient patency (primary, primary assisted, secondary) response classification (yes/ no) concerning the primary efficacy parameter and the secondary efficacy parameter on patency, as well as any data needed to define patients date of HAV failure and date of loss of patency
- Adverse event data (HAV complications)

The final decision regarding the patency outcomes and date of HAV failure/ loss of patency will be documented within a meeting minutes document. The Sponsor will review the document and verify the decision by signing the document.

The final data base closure (hard lock) will be performed afterwards.

9 Miscellaneous

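### Does the SAP leave open how early leavers count in the patency rates, and whether abandonment outranks censoring?

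*Protocol*

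**What the plan says.** Protocol 9.3 defines the three patency types, plans rates at Month 12 and at every other visit where patency is assessed, and adds: "Early discontinued patients prior to the visit of interest will be determined as being non-patent irrespective of the reason for discontinuation". Protocol 9.1 includes every patient who receives an HAV and keeps all available data from those who leave.

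SAP version 2.0, section 4.4.1, defines the patency states and the eCRF sources for them. It then writes "Data handling for this rate will be as followed" and continues: "The assignment to a patency (yes/no) (primary, primary assisted, secondary patency) will be verified during the Data Review Meeting (DRM"). Premature discontinuation is among the data to be used at that meeting. The output is described as follows: "Patency rates will be presented with frequency tabulations showing patient numbers and patency rates for Month 12", with Clopper-Pearson limits. Section 4.4.2 says that patency "rates will be presented for Months 3, 6 and 9"; section 4.4.3 says that patency "will be presented for Months 18, 24, 30, 36, 42, 48, 54 and 60". Section 8 has the meeting's patency decisions minuted: "The Sponsor will review the document and verify the decision by signing the document".

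For the Kaplan-Meier curves, method (a) reads: "Patients who die, withdraw from the study, or are lost to follow-up are censored at the day of the respective event". Method (b) treats the same patients as failures of secondary patency on that day. Abandonment is derived from an adverse event record of stenosis, thrombosis or occlusion for which the action taken was either study withdrawal or none. Section 4.4.4, on time to loss of patency by Kaplan-Meier, censors early leavers only if their HAV is still patent.

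**The concern.** Two things catch the eye.

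First, the rule for leavers stands in the protocol and in SAP version 1.0, but not in the operative SAP text. The sentence announcing data handling leads only to a data review meeting whose outcome the sponsor signs, in an open-label single-arm study. If leavers could be coded case by case, the Month 12 rate, a primary efficacy endpoint, would depend on decisions taken after the data were seen.

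Second, one record can seem to be both the failure and the reason for censoring: an occlusion with withdrawal as the action taken. The SAP does not say which date is the abandonment date. If it were the withdrawal date, method (a) read alone could censor a failed vessel. This route occurs in practice: in the earlier PAD study, CLN-PRO-V002, four of 20 patients were withdrawn after occlusion (Protocol 2.4.3). Protocol 9.3 also says that the results will be used to size later studies, so an inflated rate would carry forward.

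**Working it through.** **Inputs.** N = 15 recruited (SAP 1.5). Exact two-sided 95% Clopper-Pearson limits (SAP sections 4 and 4.4.1). Neither document gives the number of early leavers or of patency losses, so both are assumed below. The plan states no Month 12 figure to reproduce.

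**Size of the coding choice.** Assume 3 losses by Month 12, k leavers with a patent vessel, and everyone else followed to Month 12. The protocol's rule gives (15 − 3 − k)/15. Keeping the last known status gives 12/15 for any k.

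| k | Protocol rule | Last status kept | K-M method (a) | K-M method (b), secondary patency |
|---|---|---|---|---|
| 0 | 12/15 = 80.0% (51.9–95.7) | 80.0% | 80.0% | 80.0% |
| 1 | 11/15 = 73.3% (44.9–92.2) | 80.0% | 78.6–80.0% | 73.3% |
| 2 | 10/15 = 66.7% (38.4–88.2) | 80.0% | 76.9–80.0% | 66.7% |

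The ranges for method (a) cover every ordering of losses and exits. With method (b) nobody is censored before Month 12, so the estimate is the crude proportion and equals the protocol's rule. The two codings differ by k/15 whatever the number of losses; with 2 losses and k = 1, for example, 12/15 = 80.0% against 13/15 = 86.7%.

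**Is the coding open?**

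1. *Denominator.* SAP 3.3 puts every analysis on the safety set, which SAP 3.1 defines as enrolled patients who received an HAV. Protocol 9.1 agrees. Dropping leavers (11/14 = 78.6% or 10/13 = 76.9%) would contradict both documents.
2. *Numerator.* SAP section 1 says that the SAP is based on protocol version 4.0 and details its methods. The protocol's rule is explicit and covers any reason for leaving. No visible SAP sentence gives a different rule for the tables. Premature discontinuation is a listed input to the yes/no status, which is the item needed to apply the rule.
3. *Other visits.* The protocol's wording refers to whichever visit is of interest, so it also covers the rates in SAP 4.4.2 and 4.4.3.

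**Event or censoring?** SAP 4.4.4 limits censoring to leavers whose vessel is still patent. An abandoned or occluded vessel is not patent, so its loss is an event. Abandonment comes from the adverse event eCRF, which makes the adverse event date a natural reading. After thrombosis or occlusion, primary and primary assisted patency end no later than the thrombosis onset date under the SAP's own table, so only secondary patency could be affected. A stenosis without thrombosis that ends in withdrawal depends on the abandonment date for the other types too, and the same 4.4.4 limit applies.

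If one of three occlusions were nevertheless censored, with no other leavers, secondary patency would move from 12/15 = 80.0% to between 12/14 = 85.7% (censored before the two events) and 13/15 = 86.7% (censored after them). That would be a real error, but it requires ignoring 4.4.4.

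**Sponsor practice in V002.** Protocol 2.4.3 reports secondary rates of 89.5%, 84.2%, 79.0% and 73.7%. The fractions 17/19, 16/19, 15/19 and 14/19 are 89.5%, 84.2%, 78.9% and 73.7%, which match to within 0.1 point. That implies five losses, with one patient censored before the first. The same section describes five vessels finally lost: one replaced, two left occluded, and two for which intervention was refused. If the four occlusion withdrawals are among these five, they were counted as events. Censoring them would leave one event and give 93.3–94.7%, far from the reported 73.7%.

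**The case for a change.** The best argument for a change is that a SAP should stand on its own for a primary endpoint. Version 1.0 contained the sentence, version 2.0 lost it, and the dangling lead-in suggests that text was dropped. Status is set at data review with sponsor sign-off and without blinding. Method (b) does not fill the gap completely: it governs curves rather than the frequency table, and it names secondary patency only. SAP 4.4.4 is not cross-referenced from method (a).

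All of that is accurate, and a careful author would repeat the sentence. It shows that the SAP is terse, not that the analysis is undetermined: a SAP's silence does not cancel an explicit protocol rule. SAP section 10, on changes from the protocol, appears in the contents list but its text is not in the copy available here, so neither a declared change nor its absence can be asserted.

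V002 might also be cited for a large effect: at most 13/20 = 65.0% under the protocol's rule at Month 24, against 73.7% by Kaplan-Meier with deaths censored, a gap of at least 8.7 points. That compares two estimators in another study. The four occlusion withdrawals are failures under the protocol's rule and apparently were in the reported curve, so the gap mainly reflects the three deaths and does not measure the missing sentence.

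**Conclusion.** No change to the plan is needed. Protocol 9.3 together with SAP 3.1, 3.3, 4.4.1 and 4.4.4 already yields one table rule (leavers non-patent, all implanted patients as denominator) and one curve rule (loss of patency is an event; only a patent vessel is censored). Methods (a) and (b) show secondary patency under both treatments of leavers, so a reader will see how much they matter.

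The most the unrepeated sentence could move the Month 12 table is 6.7 points per leaver with a patent vessel, and only if the protocol were disregarded. For one leaver with three losses, the exact interval runs from 44.9% to 92.2%, a width of 47.3 points, and all results are declared exploratory with no hypothesis test. Ranking the frequency table above the curves would be a matter of preference.

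This conclusion assumes that analysts apply the protocol's rule where the SAP is silent, and that SAP section 10 declares no departure from it. The leaver and loss counts are illustrative; with no leavers the table codings coincide.
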